2.1 Changes to the planned analyses in the protocol

The Extension study is conducted to fulfill regulatory requirements independent of whether the Core study succeeds on its primary objective or not. As such, Type I error and power control is not a feature of the Extension study design, and the results cannot be viewed within a valid inferential context. Thus, statistical significance cannot be inferred from any analyses based upon reaching specific significance thresholds. As a result, all hypotheses testing is not aimed to claim statistical significance or superiority of one treatment group against another, but needs to be interpreted with caution.

Patients may receive study treatment up to Week 40 only, while the study is purely observational beyond this time point. Therefore, results from the analysis of “recurrence of ROP up to 52 weeks post baseline visit in the Core study” (stated in protocol Section 9.5.1) would be identical to the results performed for “recurrence of ROP up to week 40 post baseline visit in the Core study”, since recurrence (defined as intervention, i.e. study treatment, received after baseline of the Core study”) remains unchanged and such analysis at week 52 is considered not meaningful.

2.2 Data analysis general information

Three planned analyses will be performed in this study: two interim analyses and one final analysis at the completion of the study. The statistical analysis will be performed or directed by the Biostatistics & Pharmacometrics of Novartis.

Assessments documented in the database that occur as “bilateral” will be summarized and listed for each eye separately. To facilitate derivations and analysis based on eye, database records for bilateral will be split into two records containing identical information as the original record with the exception of the laterality which shall be recoded to “Right” and “Left”, respectively.

Change from baseline will only be summarized for patients with both baseline and post-baseline values for the relevant visit and will be calculated as:

Change from baseline = post-baseline value – baseline value

Descriptive statistics (mean, median, standard deviation, lower quartile (Q1), upper quartile (Q3), minimum, and maximum) will be presented for continuous variables. The number and percentage of patients in each category will be presented for categorical variables. If a confidence interval is presented for a categorical variable, then the exact Clopper-Pearson method ([Newcombe, R.G., 1998](#)) will be used to calculate the 2-sided 95% confidence interval.

This document is written in the future tense. It will be reviewed and updated (including conversion to past tense) for entry into the clinical study report (CSR) after the analysis has taken place. The analyses described in this document will be conducted using SAS version 9.4 or later.

2.2.1 General definitions

Study treatment refers to study ranibizumab in both Core and Extension studies, and laser therapy in the Core study. (Please note that laser is a study treatment in the Core study but not a study treatment in the Extension study.) In this document, patient and subject are used interchangeably throughout the document.

A patient randomized to ranibizumab in the Core study can receive switch/rescue laser therapy in either eye; a patient randomized to laser therapy in the Core study can receive switch/rescue ranibizumab 0.2 mg in either eye. The change of treatment modality from laser to ranibizumab can occur at any time in the Core study and only in Epoch 1 of the Extension study, while the change of treatment modality from ranibizumab to laser can only occur in the Core study as only ranibizumab is available as study treatment in the Extension study. No further ranibizumab treatment can be administered to the eye after it has been switched to laser. The switch of study treatment occurs when the patient first receives a treatment modality other than the modality of the first study treatment in either eye, which can occur in the Core or Extension study period.

There are three treatment arms defined by the initial treatment received at baseline of the Core study:

- 0.2 mg Ranibizumab arm (same as Ranibizumab 0.2 mg arm)
- 0.1 mg Ranibizumab arm (same as Ranibizumab 0.1 mg arm)
- Laser treatment arm (same as Laser arm)

All results will be displayed by the initial treatment received at Core study baseline. If appropriate, within each of these three treatment arms, analyses may also be conducted separately for patients who received monotherapy or who switched treatment (by eye or by patient as applicable) during the Core study.

Two baselines are defined; Core baseline and Extension baseline. For statistical purposes, the last available non-missing values collected in study CRFB002H2301 or CRFB002H2301E1 prior to or on visit 201 will be considered to be the Extension baseline values. Core baseline will be used as baseline for both efficacy and safety analyses. The Extension baseline will be used for the demographic summary of the Extension study.

2.2.1.1 Baseline definition and post-baseline definitions

All data collected after Day 1 of the Core study are defined as post-Core baseline.

All data collected after the Extension baseline visit are defined as post-Extension baseline. The study day relative to Core baseline for a scheduled or unscheduled visit which is on or after the date of first study treatment (of the Core study) in either eye is defined as

$$\text{Study day} = (\text{Date of visit}) - (\text{date of first study treatment in either eye in Core study}) + 1$$

The study day relative to Core baseline for a scheduled or unscheduled visit which is before the date of first study treatment (of the Core study) in either eye is defined as

$$\text{Study day} = (\text{Date of visit}) - (\text{date of first study treatment in either eye in Core study})$$

The study day relative to Extension baseline for a scheduled or unscheduled visit on or after Extension baseline is defined as

$$\text{Study day} = (\text{Date of visit}) - (\text{date of Visit 201 in Extension study}) + 1$$

For the purposes of classifying an eye by ROP disease status, the worst disease present in any clock hour of the eye, ranked in descending order from worse to best in [Table 2-1](#), will be used to classify the eye at Core baseline and during the study.

Plus disease is defined as vascular tortuosity and dilatation in at least 2 quadrants of the eye (International Committee for the Classification of Retinopathy of Prematurity 2005).

For the purposes of classifying a patient by ROP disease status, the worst eye ranked in descending order from worse to best in [Table 2-1](#) will be derived from the eCRF.

If both eyes have the same zone and stage, then the worst eye is the one with the greater total number of clock hours with the highest stage. If this is also the same for both eyes, then the left eye will be assigned as the worst eye.

The better-seeing eye and the worse-seeing eye at the 5th birthday visit are defined as the eye with a higher and lower ETDRS letter score, respectively. If both eyes have the same ETDRS letter score, then the left eye will be assigned as the worse-seeing eye.

The best vision of the Low Visual Acuity Testing is defined as the best assessment with an answer 'YES', in the order of 'Count fingers' > 'Hand movement' > 'Light perception'. If all assessments have answers 'No', the best vision of the Low Visual Acuity Testing is defined as 'None of the above'. If the eye had a Low Visual Acuity Testing and all assessments have missing answers, the best vision of the Low Visual Acuity Testing is defined as 'Missing'.

Table 2-1 Ranking of Retinopathy of Prematurity Disease

Zone	Stage
Any	5
Any	4
I	AP-ROP
II	AP-ROP
I	3+
I	3
I	2+
I	1+
II	3+
II	2+
I	2
I	1
II	3
II	2
II	1+
II	1
III	3+
III	3
III	2+
III	2
III	1+
III	1

Abbreviations: AP-ROP - aggressive posterior retinopathy of prematurity; ROP - retinopathy of prematurity

2.2.1.2 The last study visit

The last study visit is Visit 399 (including premature withdrawal). If the patient does not discontinue the study, Visit 399 will occur close to the patient's fifth birthday.

For the visual acuity at Visit 399, the study day will be allocated to the 5th birthday visit if the study day is before the 5th birthday and within 3 months of the 5th birthday, or if the study day is after the 5th birthday.

For all other variables except for the visual acuity, the study day for the premature withdrawal Visit 399 will be allocated to the nearest planned main visit if data for the nearest planned main visit does not already exist and if the study day is within the allocation windows of the planned main visit.

All applicable assessments will be captured by scheduled visit. [Table 2-2](#) shows the allocation windows of premature withdrawal visit to a scheduled main visit of H2301E1.

Table 2-2 Allocation of premature withdrawal visit

Scheduled main visit number	Scheduled visit study week/year	Scheduled visit window in days
202	Week 32	197 – 253
203	Week 40	254 – 323
301	Week 52	324 – (Start date of mother's last menstrual period – Core study baseline visit date+766)
302	2-year corrected age	(Start date of mother's last menstrual period – Core study baseline visit date+891) – (Start date of mother's last menstrual period – Core study baseline visit date+1131)
303	3-year corrected age	(Start date of mother's last menstrual period – Core study baseline visit date+1257) – (Start date of mother's last menstrual period – Core study baseline visit date+1497)
304	4 th birthday	(Start date of mother's last menstrual period + gestational age (in weeks) *7 – Core study baseline visit date +1341) – (Start date of mother's last menstrual period + gestational age (in weeks) *7 – Core study baseline visit date +1581)
	5 th birthday	For visual acuity: (Start date of mother's last menstrual period + gestational age (in weeks) *7 – Core study baseline visit date +1736) – End of study For variables other than visual acuity: (Start date of mother's last menstrual period + gestational age (in weeks) *7 – Core study baseline visit date +1706) – (Start date of mother's last menstrual period + gestational age (in weeks) *7 – Core study baseline visit date +1946)

2.2.1.3 Additional assessment visit schedule

The additional assessment visits of Epoch 1 are triggered by a post-baseline treatment (re-treatment with ranibizumab or switch ranibizumab treatment from study laser therapy in the Core study) (Section 6 of Protocol). When a visit as per the additional assessment schedule coincides with a visit as per the main assessment schedule, assessments have to be performed as per the main assessment schedule.

For analyses by visit, only data of planned main visits will be reported. For analyses up to a certain time point, data of both planned main visits and additional assessment visits up to that time point will be considered. All data collected at additional assessment visits will be used for analysis and listed.

2.2.1.4 Unscheduled visits

All data collected at unscheduled visits will be listed.

All safety and exposure to treatment data collected at unscheduled visits will be considered.

Other data collected at unscheduled visits will not be used for tables and graphs analyzing post-baseline data when reporting by scheduled visit.

2.2.1.5 Missing baseline data

Missing baseline data (both Core baseline and Extension baseline) will not be imputed. This includes variables which are not allowed to be collected according to local regulations (e.g. race in France).

2.2.1.6 Missing post-baseline data

Observations with values ‘not done’, ‘not evaluable’, ‘not applicable’ will be treated as missing values.

Missing efficacy data will not be imputed.

Apart from AE and concomitant medication dates, missing post-baseline safety data will not be imputed.

Missing data for other variables will not be imputed unless otherwise specified.

2.2.2 Data for permanent study treatment discontinuation

Patients that permanently discontinue study treatment will remain in the study and all planned assessments should be conducted (Section 5.6.2 of Protocol).

2.3 Analysis sets

The Extension Safety Set for this study is defined as the subset of the patients from the Safety Set of the Core study who enter this Extension study and comprises data from both the Core and Extension studies.

All analyses will be carried out on the Extension Safety Set and displayed by the initial study treatment received at the baseline of the Core study unless otherwise specified.

[Table 4-1](#) shows the protocol deviations leading to data exclusion from the analysis data set.

2.4 Patient disposition, demographics and other baseline characteristics

Outputs for subject disposition, and demographic characteristics will be reported for each treatment arm and all patients (total). Demographic and baseline characteristics will be summarized for both Core baseline and Extension baseline.

No tests for differences in demographic characteristics among treatment arms will be performed.

Relevant medical history and current medical conditions using the Core baseline will be tabulated by system organ class (arranged alphabetically) and preferred term (arranged by decreasing frequency sequentially in the ranibizumab 0.2 mg treatment arm) according to the latest MedDRA version. Separate tables will be presented for ocular and non-ocular histories and conditions. The reporting will be by patient (not eye).

The same approach will be used for the relevant medical history and current medical conditions using the Extension baseline, which will include medical history/condition collected after the last visit in Core study and before the baseline visit in this Extension study, corresponding to segment b of [Figure 2-1](#).

Partial dates of diagnosis will be imputed using imputation rules as stated in [Section 4.1.3](#).

Guidance of Data Entry rules in the Extension study eCRF which provides details on handling of Medical History in the Extension study.

- Core Medical History which is still ongoing at the time of enrollment (Baseline Visit) into the Extension study will not be reported again as Extension Medical History.
- Core Medical History which resolved before enrollment into the Extension will not be reported as Extension Medical History.
- Core Medical History which resolved before the Core End of Study visit and which reoccurred after the Core End of Study visit but before enrollment into the Extension study, will be entered as Extension Medical History. For such cases, multiple episodes of the same Medical History will appear across the Core and Extension study but with different start dates.
- Adverse Events (AEs) and Serious Adverse Events (SAEs) continuing at the end of Core study which resolved prior to Extension informed consent form date will be reported as Extension medical history with medical history ongoing status as “No”, further medical history term, preferred term (start date) should be an exact match to adverse event term, preferred term and adverse event start date. No plausible entries are accepted.
- Adverse Events (AEs) and Serious Adverse Events (SAEs) which started after end of Core study and resolved before the time of Extension study enrollment (Baseline Visit) will be reported as Extension medical history with medical history ongoing status as “No”.
- Adverse Events (AEs) and Serious Adverse Events (SAEs) which started after end of Core study and are ongoing at the time of Extension study enrollment (Baseline Visit) will be reported as Extension medical history with medical history ongoing status as “Yes”..

Tabular format for Data Entry rules in the Extension study eCRF for Medical History

Item	Started	Ended	Action for ECRF
Med Hx	before Core	Ongoing end of Core and at beginning of Ext	Don't record as MHx in Ext (MHx of Core)
Med Hx	before Core	Ongoing end of Core and finished in Gap	Don't record as MHx in Ext (MHx of Core)
Med Hx	Gap	Gap	Record as MHx in Extension (not ongoing)
Med Hx	Gap	Ongoing at beginning of Ext	Record as MHx in Extension (ongoing)
(S)AEs	Core	ongoing end of Core and finish in gap (before Ext)	Record as MHx in Extension (not ongoing)
condition	Gap	Ongoing at beginning of Ext	Record as MHx in Extension (ongoing)
condition	Gap	Gap	Record as MHx in Extension (not ongoing)

2.4.1 Patient disposition

All disposition tables will be based on the Extension safety set. Subject disposition data is collected in specific eCRF disposition pages based on the epochs (time intervals in the course of the study) as defined in the protocol; reporting of disposition data will be presented by epoch.

The Extension study period starts from Extension baseline and includes 2 epochs: post-treatment follow-up 1 and post-treatment follow-up 2.

The number and proportion of patients who completed each epoch and who discontinued the study prior to completion of the epoch will be presented. Also the number and proportion of the primary reason for not completing each epoch will be presented.

The primary reason for premature study discontinuation and permanent study treatment discontinuation will be displayed by actual treatment and overall for this Extension study.

Baseline-Failure Subjects are patients with informed consent obtained from their parent(s) or legal guardian(s) but who were discontinued at the baseline visit because they did not meet all inclusion/exclusion criteria. The number of these patients and their reasons for inclusion/exclusion failure will be summarized.

The number of patients with CSR reportable PDs according to the applicable SOP will be presented for this Extension study. The results will be grouped using the broad categories defined in the applicable SOP, which currently are:

- Eligibility: Patients who entered the trial even though they did not satisfy the entry criteria
- Withdrawal: Patients who developed withdrawal criteria during the trial, but were not withdrawn
- Study Drug: Patients who received the wrong treatment or incorrect dose
- Concomitant Medication: Patients who received an prohibited concomitant medication
- Other reportable protocol deviation

The reasons for exclusion from efficacy or safety analysis will be listed.

2.4.2 Baseline and demographic characteristics

Descriptive statistics (mean, median, standard deviation, minimum and maximum, quartiles 1 and 3) will be presented for the continuous variables. The number and percentage of patients will be presented for categorical variables.

Table 2-3 shows the allocation of baseline parameters into groups and which are displayed as continuous and/or categorical variables.

Table 2-3 Display of baseline parameters:

	Demographic	ROP characteristics and relevant medical history	Continuous	Categorical
Race	x			x

Ethnicity (based on that of mother)	x			x
Sex	x			x
Gestational age at birth (by completed weeks)	x		x	x
Chronological age at Core baseline (by weeks)	x		x	
Chronological age at Extension baseline (by weeks)	x		x	
Post-menstrual age at Core baseline (by weeks)	x		x	
Post-menstrual age at Extension baseline (by weeks)	x		x	
Corrected age at Extension baseline (by weeks)	x		x	
Birth weight (g)		x	x	x
Body length at birth (cm)		x	x	x
Head circumference at birth (cm)		x	x	x
Lower leg length		x	x	x
ROP zone by patient		x		x
ROP zone by eye		x		x
AP-ROP status by patient		x		x
AP-ROP status by eye		x		x
ROP disease status by patient		x		x
ROP disease status by eye (worst/best)		x		x
APGAR sCore at 1 minute		x	x	
APGAR sCore at 5 minutes		x	x	
Intubation requirement before enrollment (y/n)		x		x
Multiple pregnancy (y/n)		x		x
Number in multiple infants born of a multiple pregnancy		x	x	
Born in study hospital (y/n)		x		x
Time from first diagnosis of ROP to screening visit (weeks)		x	x	x
Time from ROP fulfilling treatment criteria to screening visit (weeks)		x	x	x

Chronological age and Post-menstrual age will be calculated from Core study baseline as below:

Chronological age at Core/Extension baseline (weeks) = [Core/Extension baseline visit date - (start date of the mother's last normal menstrual period + gestational age at birth*7)+1]/7

Post menstrual age at baseline (weeks) = (Core/Extension baseline visit date - start date of the mother's last normal menstrual period+1)/7

Corrected age at Extension baseline (weeks) = [Extension baseline visit date - (start date of the mother's last normal menstrual period + 40*7)+1]/7

The time from a pre-screening event (e.g. diagnosis of a condition or taking a medication) in days will be derived using the formula:

Time since <event> [days] = date of screening– date of event

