2.9.4.3 Health status

Respiratory function status:

The patient's respiratory function status will be summarized and listed for applicable visits by treatment arm.

For the Core study period, the requirement for respiratory support (other than oxygen therapy) and the requirement for oxygen therapy will be summarized. Positive end-expiratory pressure, fraction of inspired oxygen and percentage of oxygen saturation will be summarized by presenting summary statistics of values and change from Core baseline to day 169 by treatment arm.

For the Extension study period, the respiratory function status (wheezing/whistling status, number of attacks of wheezing, frequency of sleep disturbance, presence of wheezing limiting patient's speech ability, dry cough status and presence of smoker at home) will be summarized for the patients' 2 years' corrected age visit and 5th birthday visit.

Hearing function status:

The patient's hearing function status will be summarized and listed for the patients' 2 years' corrected age visit and 5th birthday visit.

Hospitalization:

Duration of hospitalization (from birth to first hospital discharge home) from the Core study and weight at the first discharge from hospital home will be summarized.

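### Birth date is rebuilt from completed gestational weeks, so chronological age can be overstated by up to 6 days and the birthday windows can sit up to 6 days early

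*SAP*

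**What the plan says.** Section 2.4.2 takes chronological age at Core and at Extension baseline as the visit date minus a rebuilt birth date, in weeks: "start date of the mother's last normal menstrual period + gestational age at birth*7)+1]/7". Table 2-3 in the same section lists the variable as "Gestational age at birth (by completed weeks", and the SAP gives no other definition of it.

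Post-menstrual age does not use gestational age: "Post menstrual age at baseline (weeks) = (Core/Extension baseline visit date - start date of the mother's last normal menstrual period+1)/7". Corrected age uses a fixed 40 weeks, so it does not use gestational age at birth either.

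Table 2-2 in section 2.2.1.2 uses the same rebuilt date for the birthday windows:

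- 4th birthday: opens at "gestational age (in weeks) *7 – Core study baseline visit date +1341" and closes at an offset of +1581.
- 5th birthday, visual acuity (VA): "gestational age (in weeks) *7 – Core study baseline visit date +1736) – End of study".
- 5th birthday, other variables: opens at an offset of +1706 and closes at "gestational age (in weeks) *7 – Core study baseline visit date +1946".

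The text above that table states the VA rule in terms of the fifth birthday itself. It accepts a value up to 3 months before the birthday, or any time after it.

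**The concern.** Completed weeks drop the odd days. Seven times the completed weeks, added to the menstrual date, gives the day on which the last full week ended, which is the day of birth only for a child born on an exact week. For every other child it falls before the birth. The error has one direction, so it does not average out over patients.

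Two things are at stake. Chronological age is reported in the demographic summary at two baselines, and in infants a few days are a visible fraction of the value. The rebuilt date also sets the window that decides whether a Visit 399 VA value counts as the fifth-birthday value, so the table and the text rule can disagree for a record near the limit.

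**Working it through.** **Inputs.** The age formulas and the completed-weeks label are from section 2.4.2. The window offsets are from Table 2-2 in section 2.2.1.2. LMP is the start of the last menstrual period, and gestational age at birth is w weeks + d days, with d = 0 to 6.

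**Step 1. Reproduce the plan's offsets.** Four years is 4 × 365.25 = 1461 days. Five years is 5 × 365.25 = 1826.25, taken as 1826.

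| Window | Arithmetic | Table 2-2 |
|---|---|---|
| 4th birthday | 1461 − 120 and 1461 + 120 | 1341 and 1581 |
| 5th birthday, other variables | 1826 − 120 and 1826 + 120 | 1706 and 1946 |
| 5th birthday, VA | 1826 − 90 | 1736 |

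All match. LMP + gestational age × 7 therefore stands in for the date of birth.

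**Step 2. Error in the rebuilt date.** True birth = LMP + 7w + d. Rebuilt birth with completed weeks = LMP + 7w. The difference is d days, always early or zero. If d is uniform on 0 to 6, the mean is (0+1+2+3+4+5+6)/7 = 3 days.

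**Step 3. Effect on chronological age.** Keeping the +1 in both versions, the overstatement is d/7 weeks: 0 to 6/7 = 0.86, mean 3/7 = 0.43.

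Example: birth at 26 weeks + 6 days (188 days), visit 70 days later, so the visit is at LMP + 258.

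- SAP formula: (258 − 182 + 1)/7 = 11.00 weeks.
- True birth date, same convention: (70 + 1)/7 = 10.14 weeks.
- Post-menstrual age: (258 + 1)/7 = 37.00 weeks.

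Post-menstrual age minus chronological age should return the gestational age. The SAP formula gives 37.00 − 11.00 = 26.00, so the 6 odd days have moved into the child's age. The true birth date gives 37.00 − 10.14 = 26.86 weeks, which is 26 weeks + 6 days.

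**Step 4. Relative size.** The SAP gives no typical age at Core baseline, so I assume 8 to 14 weeks. The mean overstatement is 0.43/8 = 5.4% down to 0.43/14 = 3.1%. The maximum is 0.857/8 = 10.7% down to 0.857/14 = 6.1%.

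**Step 5. Effect on the windows, relative to the true birthday.**

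| d | VA opens | Other 5th-birthday window |
|---|---|---|
| 0 | −90 | −120 to +120 |
| 3 | −93 | −123 to +117 |
| 6 | −96 | −126 to +114 |

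The 4th-birthday window moves by the same d days at both ends. These figures read the offsets as plain day differences. If they are study days under the inclusive rule of section 2.2.1.1, with first treatment on the baseline visit date, each limit falls one day earlier (VA: 91 to 97 days before). The 0-to-6-day shift from truncation is unchanged.

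**The case against.** The best counter-argument is that the premise is inferred. The completed-weeks label is a row in a table about display. The formulas say only gestational age at birth, or gestational age in weeks. If the stored value carries the days as decimals, the error vanishes. This stands as a condition on the finding. It does not remove the point, because the SAP defines no other gestational age and a programmer following it would use completed weeks.

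The plan may also have used the menstrual date deliberately because an exact date of birth was not available for analysis. The SAP does not list date of birth as a variable. A fifth-birthday visit and a duration such as "Duration of hospitalization (from birth to first hospital discharge home" suggest that sites know the date, but do not prove that the database holds it. The fix has to allow for this.

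The practical consequence is small. Age is summarised without tests (section 2.4), and the models in sections 2.6.2 and 4.3 use treatment arm and ROP zone, not age. Apart from VA at Visit 399, Table 2-2 allocates only premature-withdrawal visits. All of this stands.

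A reader might infer more than the document supports:

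- **That the +1 adds a further day of bias.** It is the SAP's inclusive counting, used for all three ages and for study day from baseline onward. It is a convention and not an error.
- **That every child's age is overstated.** A child born on an exact week is unaffected.
- **That children without a menstrual date lose their age and windows.** Section 2.2.1.5 is a general rule against imputing baseline data. Nothing shows that any such child exists.
- **That the windows are widened.** The bounded ones close as early as they open. Only the VA window, which runs to end of study, gains days.

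**Conclusion.** The point holds as a minor error in a stated rule. As written, the formula places birth 0 to 6 days early. Chronological age is overstated by 0 to 0.86 weeks, and the bounded birthday windows shift early by the same number of days. The VA window opens up to 6 days before its intended limit.

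This rests on two assumptions: that the completed-weeks variable of Table 2-3 is the one entered, and that gestational age was counted from the recorded menstrual date. If it was dated another way, the error could differ in size and sign. The mean of 0.43 weeks also assumes that the dropped days are uniform, and the 3 to 5% assumes a Core-baseline age of 8 to 14 weeks.

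No between-arm bias is expected, because the truncation does not depend on treatment. Only a VA record in a strip of at most 6 days, about three months before the fifth birthday, could change status, so the effect on the primary comparison is negligible. Post-menstrual and corrected age are not affected.

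**What to change.** In section 2.4.2, compute chronological age as (baseline visit date − date of birth + 1)/7. In Table 2-2, replace the rebuilt date by the date of birth in the 4th- and 5th-birthday rows and leave the offsets as they are. Keep the +1. Dropping it from chronological age alone would make post-menstrual age minus chronological age exceed gestational age by one day in every child.

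If date of birth is not held, use gestational age in weeks and days, entered as 7 × weeks + days, in the same places. If only completed weeks are held, keep the formulas and state with the reported ages that they carry a shift of 0 to 6 days, mean about 3 if uniform.

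The cost is one formula and the birthday rows of one table, or one sentence in the last case. Which version applies depends on what the database contains, and the SAP does not settle that.
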